## 4 Objectives

### 4.1 Study Objectives

Our aim is to enroll 60 subjects (30 intervention, 30 control). Because this is a pilot study, it is not fully powered to detect differences between groups. Our main objectives are as follows:

- Field test study logistics: We will record the number of families approached, screened, ineligible, refusing participation, and enrolled; rate of recruitment and referring provider/site; intervention attrition and study retention; adverse events; and collect participant feedback via detailed exit interviews.
- Optimize intervention delivery: We will collect process measures for intervention optimization including the number of contacts and length of time per contact, referrals made and resources received, time to resolution of each unmet need, and participant feedback.
- Explore putative intervention mechanisms: We will do this via participant exit interviews and parent-report questionnaires. We will power a future study for detection of target engagement using the parameters obtained. Our proposed measures of target engagement are unmet social needs (decrease expected); parent stress (decrease expected); parent activation (increase expected), and child/parent mental health service use (increase expected). These may change based on formative work and participant feedback.

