***Intervention Part 3, Resource Navigation.*** Interventionists will discuss further with families the details of specific needs indicated during screening in order to best tailor assistance provided. Based on this conversation, the interventionist may offer more intensive support navigating to certain resources for families where it is needed. Interventionists will have a companion Navigation Resource Booklet that includes workflows and algorithms to assist with referral decisions for families. The level of interventionist involvement will be based on the family's particular needs, community resources available, and a shared decision-making process between the interventionist and family. For example, some participating parents may choose to

simply contact agencies listed in the Family Resource Booklet on their own, and not request any further support from the interventionist. Other families may want more assistance contacting and accessing community resources. In these cases, the interventionist may place referrals, coordinate services, or contact community agencies and providers on behalf of the family to inquire about resources.

As a default, the interventionist will offer follow-up meetings with the participating caregiver (either in-person, by phone, or via videoconference) every two weeks until three months have passed since the randomization date. The interventionist may end the intervention period later for the participant whose needs require longer than three months to resolve. The interventionist may also end the intervention period earlier than three months for the participant if all needs mentioned by the participant have been resolved. All forms of interventionist contacts (in-person appointments, emails, phone, and text message exchanges) and community resources placed on behalf of participating families will be documented in the participant's electronic medical record and logged by the interventionist in the study record. Interventionists will also log the length of time per contact. At each contact, interventionists will also inquire about resources received since last contact, and about whether additional help is needed for that need, or other (even new) needs. They will also ask for feedback about resources received and our process for helping families. Contacts will vary in time length (e.g., 5-10 minute calls vs. 1 hour long meetings) depending on the needs of each family.

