### Research Staff-collected Process Outcomes

Research staff will collect and analyze process measures throughout the intervention period in order to optimize intervention delivery. They will record:

- 1) **Contacts:** Each contact with a parent/guardian (intervention or control) including the date, time, person who initiated contact, length of time per contact, and modality of contact (e.g. phone, zoom, in person);
- 2) **Referrals made** (including agencies, date of referral, and parent/guardian vs. staff referral)
- 3) **Resources accessed** (including specific resource accessed, resource category, date accessed)
- 4) **Needs resolved** (date at which a participant indicates they no longer need help with a need and why, e.g. they received help or they no longer need help or needed help does not exist)

Throughout the study, research staff will also maintain a record (counts only) of the number of:

- 1) Potential participants identified, by which recruitment strategy, and from which clinic;

- 2) Potential participants screened ineligible;
- 3) Potential participants eligible but refusing participation;
- 4) Participants dropping intervention before its end with reason if known;
- 5) Participants dropping out of the study before its end with reason if known.

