### **Removal of Participants**

All instances of study drop out will be documented using the Premature Termination form on REDCap, including reason for dropout, who decided the participant would drop out (participant, study staff or PI), and whether the drop out resulted from burden of intervention, study assessment, or another reason. Withdrawn participants will be encouraged to continue to participate in study assessments throughout the 1-year follow-up period in order to optimize the intention-to-treat assessment design. Participants may withdraw voluntarily at any time for any reason. Withdrawn participants will be encouraged to participate in an exit interview to provide feedback on why the intervention did not work for them and suggestions for improvement. Participants may withdraw voluntarily at any time for any reason. Participants

will also be informed during the consent process that information already collected as part of the study will remain in the study record even if they later withdraw. There are two types of participant withdrawal: “intervention withdrawal” and “study withdrawal”.

1. **Intervention withdrawal:** A participant drops out of the PRE-CARE intervention (either because they are no longer interested or because the study PI feels the intervention is no longer appropriate), but still provides the research team with post-intervention data by completing assessments at the follow-up timepoints and exit interview. Intervention withdrawal would be defined as one or more of the following: Family declines to respond to PRE-CARE screening questions; family refuses to engage with the interventionist in a discussion about unmet needs; for family decline to accept the Family Resource Booklet. If a participant responds to screening questions, discusses needs with the interventionist, and accepts the Family Resource Booklet, but declines only the optional resource navigation component of the intervention, this would not constitute an intervention withdrawal.
2. **Study withdrawal:** A participant (or provider on behalf of participant) explicitly communicates that they are no longer interested in being a part of the study at all, including future assessments and compensation. Cases of intervention withdrawal are not automatically considered to be study withdrawal unless the participant specifically states that they never wish to be contacted again by the study, or if the study investigator deems any future contact would be inappropriate.

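### Resources accessed, needs resolved and time to resolution are logged through optional intervention contacts, so they will be under-recorded in low-contact PRE-CARE families

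*Combined protocol and SAP*

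**What the plan says.** Section 4.1 lists the process measures for optimizing delivery: "the number of contacts and length of time per contact, referrals made and resources received, time to resolution of each unmet need", with participant feedback. Both the amount of contact and what followed from it are therefore in the set.

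On collection, Section 8 (Part 3, Resource Navigation) states: "At each contact, interventionists will also inquire about resources received since last contact". Section 9 (Research Staff-collected Process Outcomes) defines needs resolved as the "date at which a participant indicates they no longer need help with a need and why", and gives the window: "Research staff will collect and analyze process measures throughout the intervention period".

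The amount of contact is left to the family. Section 8 says some parents may "simply contact agencies listed in the Family Resource Booklet on their own, and not request any further support from the interventionist". Section 9 (Removal of Participants) says that if a family "declines only the optional resource navigation component of the intervention, this would not constitute an intervention withdrawal". Later meetings are offered rather than fixed: "As a default, the interventionist will offer follow-up meetings with the participating caregiver", every two weeks to three months. Sections 5 and 8 also allow the intervention to end early when all needs are resolved.

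Separately, Section 4.2.1 makes unmet social needs a secondary outcome covering the screener's needs. The Schedule of Events (Section 15) lists an unmet-needs and adequacy-of-resources questionnaire at baseline and follow-up, and Section 9 has all 60 participants assessed at 3, 6 and 12 months.

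**The concern.** A resource that a family obtains by its own call to an agency enters the log only if someone later asks. The chance of being asked rises with the number of contacts, which the family chooses and which is itself a process measure. Booklet-only families are thus the ones whose results are most likely to be missed, and parent-initiated referral, a route the plan sets out to record, is the most exposed.

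Dates are affected too. The recorded date is when the participant reports, not when the need closed. On the default schedule the two can differ by about 2 weeks. For a family seen at week 1 and next at week 13 they can differ by 13 − 1 = 12 weeks.

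This matters because optimizing delivery is a main objective (Section 4.1), Section 12.2 justifies the 30 intervention participants on that ground, and Section 12.3 uses the process measures to change the intervention during the pilot. Understated resource receipt, concentrated in families who used the booklet alone, is a poor basis for those changes.

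**Working it through.** **No figure to reproduce.** The documents give no share of self-navigating families, no expected receipt rate and no planned analysis of these measures. What follows is illustrative.

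**Assumptions, none from the documents except the 30 families:** each family has 4 needs; each need is truly met with probability p = 0.3 to 0.7 whatever the number of contacts, so there is no true dose-response; receipt times are uniform over 13 weeks; a share s = 20% to 40% of families has few contacts; the rest have 7 contacts at weeks 1, 3, …, 13 (13/2 = 6.5, so about 6 biweekly follow-ups after the first visit).

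**Step 1: recorded receipt in low-contact families.** A resource is logged only if received by the last contact, so the recorded rate is p × f, where f = (mean week of last contact)/13.
- First visit only: f = 1/13 = 0.077.
- Two contacts, the second at random among weeks 3, 5, …, 13: mean week 8, f = 8/13 = 0.615.
- Four contacts, the last of three drawn from those six: mean position 3 × 7/4 = 5.25, week 1 + 2 × 5.25 = 11.5, f = 11.5/13 = 0.885.

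**Step 2: overall recorded rate** = p × [(1 − s) + s × f]. With p = 0.5:
- First visit only: 0.5 × (0.8 + 0.2 × 0.077) = 0.408 at s = 20%; 0.5 × (0.6 + 0.4 × 0.077) = 0.315 at s = 40%.
- Two contacts: 0.462 and 0.423.
- Four contacts: 0.488 and 0.477.

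The truth is 0.50 throughout.

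**Step 3: contacts against recorded resources.** Simulation of 30 families, 2,000 runs per scenario, Spearman correlation; runs with an undefined correlation were left out.

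| Collection, low-contact families | Recorded receipt in them | Mean rho | Runs with p<0.05 |
|---|---|---|---|
| Contact log, first visit only | 2–6% | 0.50 to 0.84 | 88–100% |
| Contact log, two contacts | 18–43% | 0.21 to 0.43 | 21–67% |
| Contact log, four contacts | 26–62% | 0.06 to 0.15 | 6–14% |
| Asked of all at 3 months | 30–70% (true) | 0.00 | 4–6% |

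The recorded rates agree with Step 1: for example 0.3 × 0.615 = 18% and 0.7 × 0.615 = 43%.

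**Step 4: the opposing force.** If contacts stop once all needs are met, and no family is low-contact by choice, rho is about −0.5 even with complete recording (p = 0.7 and 0.9). With both forces and contact-only recording, rho was +0.41 (p = 0.7, 20% first visit only), +0.34 (p = 0.9, same) and −0.16 (p = 0.9, 20% with four contacts). The sign is not determined.

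**The case against.** A reader might infer that benefit is measured only at contacts, that self-navigating families will therefore show none, and that the pilot will report a false dose-response. The documents do not support this.

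- Need status is measured independently of contact, by the questionnaire given to all 60 participants. Every PRE-CARE family is also invited to an exit interview, and referrals are extracted from the medical record in both arms.
- Not asking for more support is not the same as having no further contact. Biweekly meetings are the default for every family, brief calls and texts count as contacts, and any later contact asks about the interval since the last. Four contacts leave little distortion.
- Section 12.3 plans no dose-response analysis and disclaims effect estimation. Early ending on success pushes the association the other way.
- No coding rule says that needs nobody asked about count as unresolved.

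All of this stands against the stronger reading. It does not close the gap in the logged measures. No section shows that the questionnaire records the resource, route or date for each screened need; the instrument is not reproduced, so its content is unknown rather than shown to be lacking. Medical-record referrals are not receipt. The exit interview may be refused and is meant for feedback and mechanisms. The harm needs no formal test, since simple descriptive rates would be understated and would feed into changes to the intervention.

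A fair objection to the remedy is that a need-by-need form in one arm could prime answers on the unmet-needs outcome. Giving it after the outcome questionnaires answers this at the same visit, but not fully for later visits.

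**Conclusion.** The point holds for the staff-logged process measures: resources accessed, needs resolved and time to resolution. Followed as written, the plan under-records them in low-contact families and understates the descriptive rates. Relating contact number to them can mislead in either direction.

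The size depends on two things the documents do not give: how many families self-navigate, and how often they are reached afterwards. Under the assumptions above with p = 0.5, the overall shortfall runs from about 1 to 2 percentage points (four contacts) to about 9 to 18 points (first visit only). It is large only for families with no later contact. It does not extend to the unmet-needs secondary outcome, and a false positive dose-response is a possibility rather than a prediction.

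**What to change.** - At the scheduled month-3 assessment, and at 6 and 12 months for needs still open, ask every PRE-CARE family, whatever its number of contacts, about each need from its own screener or logged later: still need help, resource received, approximate date, own or staff route.
- Give the form after the outcome questionnaires, through assessment staff who are not the interventionist. Section 9 already keeps these roles apart for assisted assessments.
- Derive the process outcomes from this form plus the contact log. Class needs with neither source as status unknown, not unresolved.
- Treat resolution dates falling between observations as interval-censored.
- State that contact counts will not be read against resources or resolution as dose-response. Fixed-time collection removes the recording artefact but not the effect of contacts ending on success.

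Cost: one short REDCap form at visits already scheduled and paid for, a few more minutes for intervention-arm parents, recalled dates for self-navigated needs, and some possible priming of later assessments.

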## 9 Study Procedures

### **Intervention Delivery:**

PRE-CARE will be delivered by a research staff member with a minimum of a Bachelors-level degree who has experience working with low-income parents of children with ADHD. The research staff will be trained by [name], the study PI, using the protocol below, to deliver the intervention. During the intervention period, research staff who are serving as interventionists will meet weekly with [name] for supervision and feedback for quality improvement.

### **Intervention Delivery Optimization:**

Based on the experiences and feedback of subjects and staff and process measures collected, we will amend our study protocol as needed in order to optimize intervention delivery throughout the study and prepare for a fully-powered RCT.

The Family Resource Booklet component of PRE-CARE intervention will be reviewed and updated by research staff at least every 2-4 weeks to ensure that all listed agencies are currently active, and that the listed contact information and eligibility criteria is accurate. RAs will remove or revise the resources in the Family Resources Booklet throughout the trial based on participant feedback. We request to be able to make these changes without protocol modifications in order to be most responsive to participant feedback and changes in the landscape of community resources, without modifying the core intervention components.

**Intervention Training:**

All interventionists will first view a series of short, pre-recorded training videos about the WE CARE social needs screening model created by [name] research group. The videos take up to 2 hours to view. Then, the PI, [name], will also conduct at least 4 hours of intervention training in workshop format with the research staff members conducting the intervention. The training curriculum will cover intervention procedures; the basics of ADHD in preschool-age children; the basics of social needs screening; principles of shared decision-making; community, hospital, and government social service and referral resources; the basics of advocacy for special education services; and motivational interviewing.

**Participant Recruitment:**

Participants will be recruited from the Boston Medical Center (BMC) Primary Care and Specialty Care Pediatric Clinics (including Developmental Behavioral Pediatrics, Pediatric Neurology, and Child Psychiatry), the BMC Family Medicine clinic, and affiliated Community Health Center, The Dimock Center. The PI will ensure that the proper approval from the director of each clinical service or health center is in place prior to beginning recruitment at each clinic. Referrals will come from 4 possible mechanisms: 1) direct provider referral from providers in the above departments; 2) self-referrals (e.g., word of mouth); 3) use of the electronic medical record (EPIC or CDW) to identify participants seen by providers in the above departments; and 4) use of referral queues to the above departments to identify participants. These recruitment strategies are outlined in more detail below.

**1) Direct provider referral.** The research team will work with physicians and clinicians to ensure that they are aware of this research opportunity in order to facilitate their ability to refer potential participants to the study team. We will advertise the study to staff/faculty by making announcements about the study at staff meetings and discussing the study with providers. The research team may also send an email to faculty or health care providers in the above mentioned Departments with information about the study as well as the contact information for the study team. Potential participants identified by clinical staff can be given research staff contact information. Interested caregivers can be given a business card which details study staff name, phone number, email address, so they can call to learn more information about the study. Potential participants identified by clinical staff can also be given a study flier, which will detail the purpose of the study, eligibility criteria, and research staff contact information. Interested caregivers will be able to call the phone number or contact the email address for the research team included on these advertisement materials in order to learn more information about the study. In addition, providers may request that study staff call the parent/guardian to invite them to participate. To refer patients to the study for study staff to contact, providers will send a message via Epic In-Basket to the study PI, research staff member, or to the Epic ADHD Pool, which goes to research staff. Messages are linked to patients charts including contact information and patient name.

**2) Self referral.** Parents who call on their own because they have heard about the study from another person or have viewed the study flyer can be screened by research staff. The study

flyer will detail the purpose of the study, eligibility criteria, and research staff contact information. Interested patients will be able to call the phone number or contact the email address for the research team included on these advertisement materials in order to learn more information about the study. IRB approved advertisements/fliers may be posted throughout Boston Medical Center or its network of affiliated behavioral health clinics with permission. IRB approved advertisements may also be placed in newspapers.

**3) Electronic medical record.** The research team may also utilize the Clinical Data Warehouse (CDW) or Epic (BMC electronic medical record) to identify 3-5 year olds with ADHD or inattention/hyperactivity symptoms who may be eligible for the study. Members of the research team will reach out to these patients' care providers to ask if the patient may be appropriate for this research study, and if they grant permission for research staff to contact the patient's guardian to invite them to participate in the study. This process of viewing patient medical records will only be used as a way to ask providers if they feel it appropriate to invite a patient and guardian to participate. It will not be used to directly contact potential participants without permission from their treating providers. With the provider's approval, the research staff will use one of several ways to invite these patients to participate.

1. The research team may ask the provider's permission to meet the patient and parent/guardian at an upcoming appointment with their provider, at which the provider can ask the guardian and patient if they would be willing to talk with research staff to learn more about the study.
2. The research team may call the parent/guardian to provide additional information about the study, review eligibility criteria, and invite them to participate. If research staff call, they will inform the parent/guardian that their provider wanted them to know about this opportunity, and that they can decline participation without affecting their clinical care at BMC. Research staff will explain the study further and perform additional screening for those interested.
3. The research team may send a letter to the parent/guardian's home describing the study and inviting the parent/guardian to participate. If research staff send a letter, this letter will inform them that their provider wanted them to know about this opportunity, and that they can call to decline participation or they may receive a phone call to provide more information and invite them to participate (see above).

**4) Referral Queues.** Parent/guardians of potential participants referred electronically to any of the above clinics for attention or hyperactivity concerns may be invited to participate. Research staff will routinely review the following referral queues in the electronic medical record: Child and Adolescent Psychiatry, Pediatric Integrated Behavioral Health, and Developmental and Behavioral Pediatrics. These referral queues are lists of patients referred to each service by providers at Boston Medical Center and affiliated pediatric practices. Research staff will request permission from either the clinic director, medical director, or designated clinical provider responsible for triaging referrals before reaching out to patients identified by reviewing referral queues. This will take the place of contacting the referring provider for permission, given that providers may be from a practice outside of the main hospital who are not aware of the study.

When they call, staff will make clear to patients that their participation in the study will not affect their wait time nor the care they receive from the clinic.

Upon calling the study staff for scheduling or being called, interested participants will be asked to complete a brief screening interview to determine eligibility using the phone script provided with this IRB application.

